### 3.1.1 Zenith® p-Branch™

The Zenith® p-Branch™ is a modular system (Figure 3.1) constructed of full-thickness woven polyester fabric sewn to self-expanding stainless steel and nitinol Z-stents, and is introduced using the Zenith® preloaded delivery system (Figures 3.2 and 3.3). Three fenestrations and a scallop in the graft material preserve blood flow to the renal and visceral vessels. The two renal artery fenestrations are conical-shaped and may be manipulated to accommodate a range of renal anatomies with a single design. The endovascular graft is available in two fenestration/scallop configurations (A and B) to provide an optimal fit for individual patient anatomies (Figures 3.4 and 3.5). Refer to the Manufacturer's Instructions for Use (IFU) for the device sizes available and planning and sizing information for the clinical investigation.

**Figure 3.2.** Zenith® preloaded delivery system showing preloaded nitinol wire.

[figure not shown]
**Figure 3.3.** Detail of the release handles of the Zenith® preloaded delivery system.

Configuration A:

- Celiac scallop: 20 mm wide, centered at 12:30 o'clock (15°) 11 mm above SMA;
- SMA fenestration: 8 mm diameter, located at 12:00 o'clock (0°);
- Right pivot (renal) fenestration: 6 mm inner and 15 mm outer diameter, 5 mm deep, oriented at 9:30 o'clock (285°), 12 mm below SMA (center-to-center);
- Left pivot (renal) fenestration: 6 mm inner and 15 mm outer diameter, 5 mm deep, oriented at 2:30 o'clock (75°), 12 mm below SMA (center-to-center).

[figure not shown]
Configuration B:

- Celiac scallop: 30 mm wide, centered at 12:30 o'clock (15°), 9 mm above SMA;
- SMA fenestration: 8 mm diameter, located at 12:00 o'clock (0°);
- Right pivot (renal) fenestration: 6 mm inner and 15 mm outer diameter, 5 mm deep, oriented at 9:30 o'clock (285°), 16 mm below SMA (center-to-center);
- Left pivot (renal) fenestration: 6 mm inner and 15 mm outer diameter, 5 mm deep, oriented at 2:30 o'clock (75°), 20 mm below SMA (center-to-center).

**Figure 3.4.** Configuration A fenestration locations.

\*For 36 mm diameter grafts only

**Figure 3.5.** Configuration B fenestration locations.

\*For 36 mm diameter grafts only

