### *Anatomical Criteria*

[figure not shown]
Zenith® p-Branch™ endovascular graft configuration A or B will be chosen in accordance with the following criteria. All radial measurements are calculated assuming the SMA position is 12:00 o'clock (0°). Refer to the Investigator's Brochure for more details about the anatomical criteria.

1. Criteria for configuration A (renal fenestrations at same longitudinal level):
  - a. The celiac artery arises from the aorta between 11:30 o'clock and 1:30 o'clock (345° and 45°) or arises above the top of the graft;
  - b. The SMA is  $\geq 11$  mm distal to the celiac artery (unless the celiac artery is occluded or expendable);
  - c. Longitudinal positions of renal arteries arise 4.5 mm – 19.5 mm distal to the SMA;
  - d. The circumferential location of the right renal artery can range between 8:30 o'clock and 10:30 o'clock (255° and 315°) and the circumferential location of the left renal artery can range between 1:30 o'clock and 3:30 o'clock (45° and 105°) (assuming the endovascular graft diameter is approximately 30 mm).
2. Criteria for configuration B (left renal fenestration lower longitudinally than right renal fenestration):
  - a. The celiac artery arises from the aorta between 11:00 o'clock and 2:00 o'clock (330° and 60°) or arises above the top of the graft;
  - b. The SMA is  $\geq 9$  mm distal to the celiac artery (unless the celiac artery is occluded or expendable);
  - c. Longitudinal position of the right renal artery arises 8.5 mm – 23.5 mm distal to the SMA;
  - d. Longitudinal position of the left renal artery arises 12.5 mm – 27.5 mm distal to the SMA;
  - e. The circumferential location of the right renal artery can range between 8:30 o'clock and 10:30 o'clock (255° and 315°) and the circumferential location of the left renal artery can range between 1:30 o'clock and 3:30 o'clock (45° and 105°) (assuming the endovascular graft diameter is approximately 30 mm).

[figure not shown]

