## 3.3 Product Identification and Tracking

The identification and labeling of the products under investigation are outlined in the Investigator's Brochure and Manufacturer's Instructions for Use.

Products under investigation will be tracked throughout the course of the clinical investigation through use of a Product Log, upon which lot numbers, quantity, and disposition of product will be recorded. Product Logs will be maintained in the site's Investigator File. Additionally, the quantity(s), size(s), and lot number(s) of products used in patients will be recorded on case report forms (CRFs).

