## 7.2 Point of Enrollment

Point of enrollment will be based on the intent-to-treat population and is defined to include any patient for whom the treatment procedure is initiated. More specifically, the patient would be included in the intent-to-treat population upon procedure initiation (i.e., cutdown or initiation of percutaneous access). Informed consent will be obtained and assessment of the patient's conformance to the inclusion/exclusion criteria will occur prior to the procedure.

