## 8.0 Statistical Considerations

### 8.1 Hypothesis to be Tested

The primary hypothesis will assess the treatment success rate evaluated at 12 months for the Zenith® p-Branch™. [REDACTED]

[REDACTED] a [REDACTED] performance goal of 80% has been established. The performance goal will be said to have been met provided that the null hypothesis is rejected in favor of the alternative with a one-sided exact binomial test at the 0.05 level. The null ( $H_0$ ) and alternative ( $H_A$ ) hypotheses are expressed as follows, where  $\pi$  is the proportion of patients treated with the Zenith® p-Branch™ with treatment success at 12 months:

Null Hypothesis: The 12-month treatment success rate for patients treated with the Zenith® p-Branch™ does not meet the performance goal (80%).

$$H_0: \pi \leq 80\%$$

Alternative Hypothesis: The 12-month treatment success rate for patients treated with the Zenith® p-Branch™ meets the performance goal (80%).

$$H_A: \pi > 80\%$$

The safety and effectiveness of the Zenith® p-Branch™ will be established if the null hypothesis is rejected in favor of the alternative at a type I error rate of 0.05 (one-sided). This analysis will be performed on the intent-to-treat population.

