### 8.2 Statistical Analysis

Statistical analyses will be performed using SAS® for Windows® (release 9.3 or higher) or other widely accepted statistical software. Descriptive summaries will be provided where appropriate for each of the primary and secondary endpoints. In general, summaries will be completed over the total population. Continuous variable summaries will include the number of subjects (N), mean, standard deviation, minimum, and maximum. Categorical variable summaries will include the frequency and percentage of subjects who are in the particular category. Survival analysis techniques such as Kaplan-Meier or Cox

Proportional Hazards will be incorporated if censoring of data occurs.

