### 8.3 Sample Size Calculation

[REDACTED]  
[REDACTED]  
[REDACTED]  
[REDACTED] With a clinically relevant margin of 10%, [REDACTED]  
[REDACTED]  
[REDACTED]

[REDACTED] Thirty-four (34) patients are necessary to assess the primary hypothesis, under an expected 12-month treatment success rate of 97.4% [REDACTED]  
[REDACTED], with a one-sided exact binomial test, at a Type I error rate of 0.05 and a power of 0.8. A sample size of 80 patients will be enrolled to account for possible loss to follow-up while also ensuring sufficient use of both p-Branch graft configurations.

No more than 20 patients (i.e., 25% of total enrollment) will be enrolled at any one site [REDACTED]  
[REDACTED]  
[REDACTED]

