#### 8.5 Site-level Poolability

Poolability of data from multiple sites will be verified by examining the primary endpoint among sites. Site-level poolability will be considered appropriate provided that this measure is similar among sites. It is expected that some sites may have too few patients to provide reasonable site-level estimates of the primary endpoint. Pooling of this information will be explored based on hospital size (annual discharge and number of beds), type of hospital (community versus teaching), and other group-wise strategies. Should one or more sites differ from the rest, then subsequent analyses will include the discriminating covariate or a covariate to distinguish between the unusual site(s) and those sites that are considered poolable.

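### Does enrolling 80 patients partly to cover both graft configurations oblige the plan to pre-specify 12-month success by configuration?

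*Combined protocol and SAP*

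**What the plan says.** Section 8.3 gives 34 as the number of patients needed for the primary hypothesis (expected success 97.4%, one-sided exact binomial test, alpha 0.05, power 0.8). It raises enrolment to 80 "to account for possible loss to follow-up while also ensuring sufficient use of both p-Branch graft configurations". In the visible text it neither quantifies sufficient use nor states how it will be judged.

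Section 8.1 sets an 80% performance goal for the p-Branch as a single device. Safety and effectiveness "will be established if the null hypothesis is rejected in favor of the alternative at a type I error rate of 0.05", one-sided, in the intent-to-treat population. Section 8.2 provides descriptive summaries of the primary and secondary endpoints where appropriate, and adds: "In general, summaries will be completed over the total population". Section 8.5 states: "Poolability of data from multiple sites will be verified by examining the primary endpoint among sites". The groupings it names (hospital size, hospital type and similar) are ways to combine small sites.

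Section 3.1.1 describes the two configurations. They differ in celiac scallop width (20 mm in A, 30 mm in B) and in the level of the renal fenestrations. Its anatomical criteria state that the "endovascular graft configuration A or B will be chosen in accordance with the following criteria"; those criteria are vessel positions.

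**The concern.** Configuration is given as a reason for the sample size, yet it appears nowhere in the visible analysis sections. The plan checks whether hospitals can be pooled, but not whether two graft geometries can. The primary endpoint includes outcomes tied to the fenestrations: patency of the targeted vessels at deployment, and Type III endoleak, whose definition in Appendix C includes leakage around fenestrations. A difference between A and B is therefore plausible.

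If one configuration were used in a minority of patients and did worse, the pooled test could pass with little evidence about it. A by-configuration result that is not planned in advance could be left out, or shown only after the data are known.

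**Working it through.** **The plan's own figure.** The critical value is the smallest r with P(X ≥ r | N, 0.80) ≤ 0.05, and power is P(X ≥ r | N, 0.974).

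- N = 34: r = 32, alpha 0.0226, power 94.2%. So 34 meets the stated requirement.
- It is not the smallest such N. N = 22 already gives r = 21, alpha 0.048, power 88.9%. Redacted text beside the figure may explain the choice, and nothing here depends on it.
- N = 80: P(X ≥ 70 | 0.80) = 0.0565 and P(X ≥ 71 | 0.80) = 0.0287. The test passes at 71 or more; power at 97.4% exceeds 0.999.

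**How much of the increase is due to configuration.** For attrition alone to take 34 to 80, loss would have to be 1 − 34/80 = 57.5%. With assumed losses of 10% and 30%, 34/0.90 = 37.8 and 34/0.70 = 48.6, so 38 to 49 patients. At those rates most of the increase does rest on the configuration reason.

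**What the pooled test can miss.** The documents give neither the A/B split nor the rates by configuration, so these are assumptions, with all 80 outcomes known. Let n patients have the worse configuration with true success p, and let the other 80 − n have 97.4%. Then

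P(pass) = Σ_k P(K = k; 80 − n, 0.974) × P(M ≥ 71 − k; n, p).

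The true overall rate is [(80 − n) × 0.974 + n × p] / 80; for n = 16 and p = 0.70 it is (62.336 + 11.2)/80 = 91.9%. "Pass, low" (my label) means that the pooled test passes while the worse configuration's observed rate is below 80%.

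| n | p = 70%: overall | pass | pass, low | p = 85%: overall | pass | pass, low |
|---|---|---|---|---|---|---|
| 8 | 94.7% | 99.4% | 74% | 96.2% | 99.9% | 34% |
| 16 | 91.9% | 90.9% | 66% | 94.9% | 99.4% | 20% |
| 20 | 90.6% | 79.6% | 56% | 94.3% | 98.7% | 16% |
| 24 | 89.2% | 64.1% | 53% | 93.7% | 97.5% | 26% |
| 32 | 86.4% | 32.4% | 21% | 92.4% | 92.7% | 13% |
| 40 | 83.7% | 12.2% | 3% | 91.2% | 84.1% | 2% |

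The true overall rate exceeds 80% in every row, so no pass in this table is a false positive for the hypothesis in Section 8.1. The right-hand block shows the opposite risk: both configurations truly meet the goal, yet a split table would often show one of them below it.

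**What a split would deliver.** Take 62/64 in one configuration and 11/16 in the other (total 73, a pass). The exact 95% intervals are 89.2% to 99.6% and 41.3% to 89.0%. The difference is 28 points (Newcombe interval 9 to 53). The lower configuration's interval still contains 80%. Over the six sizes, a two-sided 5% Fisher test has power 66% to 93% for 97.4% versus 70%, but only 27% to 45% for 97.4% versus 85%. A non-significant result would not show similarity.

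**The case for a change.** The strongest case for a change is that most of the extra enrolment was justified by configuration, that the two geometries bear on fenestration-related components of the endpoint, and that a pre-specified table costs a few sentences. With 16 of 80 patients in a configuration at 70%, the pooled test still passes 90.9% of the time. Fixing the table in advance would also settle how to classify patients whose graft is never deployed. Under Section 7.2 "the patient would be included in the intent-to-treat population upon procedure initiation", whereas Section 3.3 lists only that quantity, size and "lot number(s) of products used in patients will be recorded on case report forms".

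Part of this stands. No visible passage commits to 12-month success by configuration, and permission to split is not a commitment to do so. The rest is weaker:

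- Sufficient use can mean exposure to each design. Enrolling 80 serves that aim without any comparison, so this is an omission and not a contradiction.
- The 70% scenario has no basis in the documents.
- Configuration follows vessel anatomy, so an A-minus-B difference cannot separate the graft from the patient who needed it.
- Section 3.3 describes product tracking and is not a full list of case report form fields. Section 6.4 also collects deployment information, and Section 7.4 completes planning and sizing before the procedure. That planned configuration cannot be recovered is speculation.
- That the result would go unreported is likewise conjecture.

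**Conclusion.** No change follows. Followed as written, the plan gives a valid test of the 12-month success rate for the device as a whole, with an exact alpha of 0.0287 at N = 80. A by-configuration summary would leave N, alpha and the primary decision as they are. It is a descriptive table of the kind Section 8.2 already allows, and an analyst with two labelled configurations would ordinarily produce it.

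If it is produced, three cautions apply. Configuration is confounded with anatomy. A small group can fall below 80% by chance even when its true rate is above the goal (a pooled pass with such a result has probability 2% to 34% at an assumed true 85%). A non-significant difference does not show that A and B perform alike.

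The pass probabilities rest on assumed splits of 8 to 40 patients, assumed rates of 70% or 85% against 97.4%, and complete outcome data. The reading of the plan is limited to the visible text: the redacted parts of Sections 8.1 and 8.3 may say more about how the configurations are handled.

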### 8.4 Missing Data

Missing data will be addressed using three primary strategies: 1) estimating missing data with the best available data, 2) case deletion, and 3) multiple imputation. The first strategy may be used for missing imaging data. Previous clinical study experience suggests that some portion of the imaging data may not meet the criteria for accurate review by the core laboratory; however, it is recognized that the investigator uses this information to provide the best possible care for the patient. Therefore, it is reasonable to substitute any missing core laboratory measurements with the corresponding measurements made by the investigator or institutional staff. In addition, the absence or presence of clinical sequelae may supplement the required missing core laboratory assessment of device performance. This strategy is a best approximation of the missing data value.

The second strategy is case deletion. If the amount of missing data does not result in a reduction of analyzable patients to a number that is below that which is required for sufficient statistical power of the

primary endpoints, then case deletion will be the method of choice for that analysis.

The third method is multiple imputation. This method will be used to predict missing endpoint or covariate data for any reason, including patient lost to follow-up. It may be that the primary study endpoints depend upon certain covariates; therefore, it may be possible to model study endpoints, given a series of related covariates. This model-based imputation exercise may provide approximations of the missing data that can be utilized in estimating event rates and confidence bounds.

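### Section 8.4 lets absence of clinical sequelae stand in for a missing core-laboratory assessment and does not exclude the imaging-defined parts of the primary endpoint

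*Combined protocol and SAP*

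**What the plan says.** Section 8.4 lists three strategies: best available data, case deletion and multiple imputation.

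- **Best available data.** "The first strategy may be used for missing imaging data". It has two parts. The plan calls it reasonable to "substitute any missing core laboratory measurements with the corresponding measurements made by the investigator or institutional staff". It then adds that "the absence or presence of clinical sequelae may supplement the required missing core laboratory assessment of device performance". The paragraph ends: "This strategy is a best approximation of the missing data value".
- **Case deletion.** If enough analysable patients remain for power, "then case deletion will be the method of choice for that analysis".
- **Multiple imputation.** "This method will be used to predict missing endpoint or covariate data for any reason, including patient lost to follow-up".

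The section does not define device performance or analysable, and does not say whether a patient filled under the first strategy counts as analysable. Section 8.1 tests success against 80% "with a one-sided exact binomial test at the 0.05 level" and adds: "This analysis will be performed on the intent-to-treat population".

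On the endpoint, Section 6.4 assesses growth above 0.5 cm from the maximum diameter on follow-up CT. Section 6.3.1 counts Type I and III leaks that need intervention after discharge, including those picked out for treatment on the 12-month CT.

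**The concern.** Using a site reading when the core laboratory cannot read an image is sensible, because a measurement still exists. The sentence on sequelae is different. It is not tied to the existence of any image, and it allows absence of sequelae to count as evidence. Growth above 0.5 cm is defined by a CT diameter, and a leak first found on the 12-month CT is by definition an imaging finding. A patient can have either and feel well, so absence of symptoms is weak evidence of freedom from both.

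If such a patient is filled in as a success, some real failures become successes and the observed rate rises above what complete imaging would show. The trial is unblinded and single-arm, and one success count decides it. As written, the same unimaged, symptom-free patient could be scored a success, deleted or imputed, and that choice should not be open once data are seen.

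**Working it through.** **Inputs from the documents.** Goal 80%, one-sided exact binomial test at 0.05 (8.1); 80 enrolled, 34 stated as necessary, expected success 97.4% (8.3). The documents give no figure for missing images or for the share of failures visible only on imaging (the silent share), so both are assumed and varied.

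**The plan's figure of 34.** At n=34 the test passes with 32 or more successes: P(X≥32 | 0.80)=0.0226, and power at 97.4% is 0.942. So 34 is sufficient for 80% power. The legible inputs reach that power at n=22, but text around the calculation is redacted, so nothing is inferred from the difference. Up to 80−34=46 patients could be missing before deletion stops being preferred.

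**Full-set cut-off.** P(X≥71 | 80, 0.80)=0.0287 and P(X≥70 | 80, 0.80)=0.0565, so 71/80 is needed.

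**All unimaged patients symptom-free.** With m unimaged, the fill needs 71−m successes among the 80−m imaged. Deletion needs the exact cut-off for 80−m.

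| m | Imaged | Needed, deletion | Needed, fill | Counts where verdict differs |
|---|---|---|---|---|
| 4 | 76 | 67 | 67 | none |
| 8 | 72 | 64 | 63 | 63 |
| 12 | 68 | 61 | 59 | 59, 60 |
| 16 | 64 | 57 | 55 | 55, 56 |

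Over m=0 to 20 there is no split count at 0–4, one at 5–11, two at 12–17 and three at 18–20. At m=8, 63/72 gives p=0.0689 and 71/80 gives p=0.0287.

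**Eight unimaged at random.** Let t be the true success rate and g the silent share. Imaged successes are Binomial(72, t). Overt failures among the 8 are Binomial(8, (1−t)(1−g)) and stay failures under the fill; the rest are scored successes. Deletion drops all 8.

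| Silent share | Change from deletion to fill | t=85% | t=88% | t=90% |
|---|---|---|---|---|
| 25% | fail to pass | 4.5% | 6.6% | 6.0% |
| 25% | pass to fail | 2.5% | 2.7% | 1.9% |
| 50% | fail to pass | 6.3% | 8.5% | 7.4% |
| 50% | pass to fail | 1.2% | 1.3% | 0.9% |
| 100% | fail to pass | 11.7% | 14.0% | 11.2% |
| 100% | pass to fail | 0 | 0 | 0 |

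At 85% and 90% themselves, fail-to-pass is 4.5–7.4% for silent shares of 25–50%; the peak lies between them. A reverse case: 64/72 passes (p=0.035), but two overt failures among the 8 give 64+6=70/80, which fails (p=0.0565). With all 8 silent, the split chance is 0.7% at t=95% and 0.01% at 97.4%.

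**Type I error under the fill.** With missing rate m at random, the filled success rate is t+(1−t)·g·m. At t=0.80, P(X≥71 | 80, 0.80+0.20·g·m) is:

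| Silent share | 10% missing | 20% missing | 30% missing |
|---|---|---|---|
| 10% | 3.2% | 3.5% | 3.8% |
| 25% | 3.6% | 4.6% | 5.7% |
| 50% | 4.6% | 7.1% | 10.7% |

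Complete data give 2.9%. The error reaches 5% when g·m=0.0595, which is missing imaging of about 59%, 24% or 12% for silent shares of 10%, 25% or 50%.

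**The case against.** The strongest reply is that context narrows the sentence. Section 8.4 introduces the first strategy for images that exist but that the core laboratory cannot read, and names patients lost to follow-up under imputation. Only measurements may be substituted, and growth is a measurement; sequelae may only *supplement* an assessment. Device performance might mean migration, patency or integrity, which are descriptive secondary endpoints. This is a fair reading, and the sponsor may intend it. It is not written down: no component is excluded, no image is required first, and the result is described as an approximation of the missing value.

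Missing imaging is also limited already. Visit windows are guidelines, so late scans count (7.6); duplex ultrasound with non-contrast CT is allowed for some patients (Table 6.1); the 6-month CT informs growth; and a leak already treated is known without a later image. All of this stands and keeps the problem small.

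A reader might infer four stronger things that the documents do not support:

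- That the plan will score unimaged, symptom-free patients as successes. It permits this but does not say so.
- That the fill always favours the device compared with deletion. That holds only if every unimaged patient is free of overt failure; otherwise reverse splits occur.
- That the unstated order of fill and deletion matters to the 34-patient trigger. More than 46 of 80 would have to be missing.
- That multiple imputation must replace deletion. Deletion is the plan's stated preference, and changing it is a debatable trade-off.

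**Conclusion.** The point holds as a gap in wording that should be closed before analysis. Section 8.4 leaves open a fill that, compared with complete imaging, can turn silent failures into successes.

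The consequence is confined to borderline results. It is nil with 0–4 unimaged patients who are all symptom-free, and negligible near 97.4%. At true success of 85–90% with 8 unimaged, it is a verdict change in several percent of trials, mostly but not only in the device's favour. Type I error exceeds 5% only when silent share times missing rate is above about 0.06.

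The split counts and p-values for symptom-free patients are exact. The split probabilities and type I figures rest on assumed missing rates, assumed silent shares and images missing at random. The case is clearest for growth; for endoleak it covers only leaks that would first be found on the 12-month CT.

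**What to change.** Add to Section 8.4, for the primary endpoint:

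1. Site readings of existing images may replace missing core-laboratory readings, including late scans and the Table 6.1 duplex and non-contrast CT alternative.
2. Presence of sequelae may support a failure. Absence alone may not establish freedom from growth or endoleak when there is no usable image.
3. Patients without a usable image and without a documented failure are missing, not analysable successes. They go to the plan's own deletion or imputation step under a rule fixed in advance.

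Report the method not chosen as a sensitivity analysis, with missing-as-failure labelled a worst-case bound. It is too harsh for a decision rule: P(X≥71 | 80, 0.974·(1−m)) is 0.47 with 10% missing and 0.01 with 20%.

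If deletion stays primary while documented failures are kept, disclose the downward bias. The analysed rate is t(1−m)/[t(1−m)+(1−t)(1−m)+(1−t)m(1−g)]. For t=0.90, m=0.2, g=0.5 (assumed) it is 0.72/(0.72+0.08+0.01)=88.9%, and the chance of passing is 0.55, against 0.65 with random deletion and 0.72 with complete data. At 97.4% the rate becomes 97.1% and the chance of passing is 0.999. Making multiple imputation primary is optional. If it is chosen, state in advance how imputed datasets are combined, because the exact test takes a single integer count.

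The cost is a few sentences, a little more analysis and possibly a slightly lower observed rate.
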